Bite elevation until reaching a min. 2 mm interocclusal distance and the lowest possible incisor distance with a lower jaw advancement of 5 mm with insertion of the MAD up to a final titrated mandibular advancement in the therapy phase.

Group strength: 97 patients per group (194 patients in total)

Description of the recruitment:

Patients are recruited at 7 dental or oral surgery clinics that specialize in the treatment of OSAS patients through MAD and are networked with referring sleep medicine centers.

Inclusion criteria:

- Patients with medical indication for mandibular protrusion (MAD) due to OSAS
- Therapy request for primary ronchopathy
- Age \geq 18 years and \leq 75 years
- BMI \leq 35
- Mandible protrusion of min. 5 mm possible (titration starts at 5 mm)
- At least 8 teeth or 4 implants per jaw
- Fixed dentures and stable, removable partial denture
- at least support up to the area of the 2nd premolars on both sides
- Business ability and the existence of the signed declaration of consent

Exclusion criteria:

- Polyarthritis
- Fibromyalgia, neuralgia
- Central sleep apnea syndrome
- untreated generalized periodontitis PSI > 2
- Chronic dysfunctional pain after GCPS grade 3-4
- Age: <18 years or > 75 years
- long-term use of psychotropic and analgesics (> 4 weeks)
- pregnancy
- Participation in another interventional clinical study (currently up to three months before inclusion)

Experimental procedure

Calibrating the examiner

All Dentists will be trained and calibrated by the study leader prior to the start of the study in the investigation tools and the data collection. Training Center is the practice of Dr. med. med. Dr. med. dent. [name], [name]. At a still to be determined weekend, all the doctors are instructed in the course of the investigation and the questionnaire survey explained. Furthermore, the clinical functional examination will be demonstrated and subsequently practiced by the study physicians. All the doctors are calibrated to the palpation pressures to be applied and the overruling determined in a final test.

Sleep Laboratory

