All patients received a structured general and somnological anamnesis and examination (height, weight, BMI, ESS, STOP-BANG, PSQI) in a first visit to the sleep laboratory. In addition, a stationary polysomnography or an outpatient polygraphy was performed there. Patients were referred to specialist dental practices for the preparation and integration of a MAD based on the diagnosis of sleep medicine for treatment of sleep apnea syndrome or snoring.

Baseline examination

Patient history and the dental status and periodontal screening index (PSI) are used to check inclusion and exclusion criteria for splint therapy. Subsequently, a functional status, occlusion protocol clinical and digital (GEDAS, Greifswald Digital Analyzing System), the questionnaires for pain chronification (GCSP) and quality of life (oral health impact profile, OHIP-5) are included.

To assess the health of the teeth and to ensure the success of treatment, an X-ray survey (panoramic radiograph) must be available before the treatment, which is not older than 6 months. Such an X-ray photograph can be made by the dentist or the specialized dental practice.

The functional status is determined by means of a standardized functional finding (DC / TMD). The questionnaires are based on validated recommendations. All examination procedures are part of the routine patient diagnostics, which have been standardized for the individual practices for this project.

Randomization

The randomized grouping into blocks at a ratio of 1: 1 takes place over sealed envelopes containing the allocation key for the respective MAD. The assignment is stratified according to gender because gender is a strong predictor of sleep disorders and also temporomandibular dysfunctions.

Impression taking

Subsequently, the upper and lower jaws are molded to make the respective therapeutic splints and the protrusion registrations are taken. The starting position of the mandibular protrusion is set to 5 mm by default.

Integration of the MAD (start of treatment)

The laboratory-made MAD (F-MAD / H-MAD) is integrated (with a mandibular protrusion of 5 mm) and checked for a comfortable fit. Here, we paid attention to a

surface contact between OK-UK splint, and a tension-free fit of the splint portions on the rows of teeth. If necessary, interfering contacts are ground in. The patient is instructed to always wear the splint during sleep.

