All patients receive an extended guide to jaw gymnastics with the instruction to do it in the morning after waking up and in the evening before falling asleep.

First control appointment (4 weeks after incorporation)

Four weeks after incorporation, the titration phase begins, d. H. the slow adjustment of mandibular advancement to optimize sleep medical parameters while minimizing unwanted side effects. The feed rate should be adjusted until clinical and sleep medical parameters are optimal or the patient can no longer tolerate further advancement.

The functional findings, the occlusion protocol, the questionnaires ESS, OHIP-5 and PSQI are collected.

Second control appointment (6 months after start of therapy)

Six months after the start of treatment, another examination is carried out in which the functional findings, the occlusion protocol and the questionnaires ESS, OHIP-5 and PSQI are collected.

Third control appointment (12 months after start of therapy)

A third check is made 12 months after the start of therapy. The functional findings, the questionnaires ESS, OHIP-5 and PSQI, the occlusion protocol, the bite registration for scanning and contact point analysis (GEDAS, Greifswald Digital Analyzing System) are collected.

Fourth control appointment (24 months after start of therapy)

The last examination is 24 months after the start of therapy. The functional findings, the questionnaires ESS, OHIP-5 and PSQI, the occlusion protocol, the bite registration for scanning and contact point analysis (GEDAS, Greifswald Digital Analyzing System) and new models are collected.

Sample size estimation

Determine the required sample size based on the numerical pain scale 0-10 for the primary target variable. Norms are pain scores of 3-5 (myofascial pain) in patients with temporomandibular dysfunction (TMD). To determine a mean difference of 1 level (standard deviation of 2) (1, 2) between the MAD, they must each comprise 78 patients.

Test method:

Wilcoxon-Mann-Whitney test with a two-sided $\alpha = 0.05$, a power = 0.90 assuming the family of logistic distributions (G * Power, version 3.1.)

The net sample consists of 156 persons. The annual dropout is 10% (3), so that for a study period of 2 years a total sample of 194 persons must be calculated (194 - 20 = 174 after 1 year, 174 - 18 = 156 after 2 years).

Statistical evaluation

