The evaluation of the primary (and also the secondary) target variable is carried out according to the power analysis using ordinal regression as a generalization of the Wilcoxon-Mann-Whitney test. Adjustments are made according to sex as a stratification variable, age ("restricted cubic splines" with 3 nodes, which requires 2 coefficients), the baseline value of the respective target variable, the centers, the school education and, if appropriate, the blocks of randomization.

The intention-to-treat analysis set includes all patients assigned to one of the two groMAD and the built-up track; the "per protocol" set includes all patients with supported splints, primary target size data at 24 months and no relevant deviations from the study protocol. Sensitivity analyzes are performed with replacement of missing values via multiple imputation.

An interim evaluation is not planned.

Subgroup analyzes are not planned.

The 95% confidence interval is interpreted; the list of primary and secondary target sizes listed above allows $\alpha = 0.05$ to be left uncorrected (Cook & Farewell) (4).

At the University Medicine Greifswald, Center for Dental, Oral and Maxillofacial Surgery (ZZMK) the blinded evaluation of the data takes place.

This study is conducted with particular attention to the contents of the following laws and guidelines:

- Declaration of Helsinki in its current version (Fortaleza, 2013)
- Medical Devices Act - MPG
- Medical Device Operator Ordinance - MPBetreibV
- State Data Protection Act - DSG M-V
- General Data Protection Regulation - EU GDPR

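### The primary pain model leaves out baseline jaw status, which is examined before randomisation; one prespecified term could add a little power at almost no cost

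*Combined protocol and SAP*

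**What the plan says.** The Statistical evaluation section of the combined protocol and SAP analyses the primary and secondary outcomes by ordinal regression. It adjusts for sex, age as a three-knot spline, and "the baseline value of the respective target variable, the centers, the school education and, if appropriate, the blocks of randomization". For the primary outcome, the baseline term is orofacial pain on the 0 to 10 scale. No jaw finding is listed for that model.

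The Baseline examination section, which precedes Randomization, says: "The functional status is determined by means of a standardized functional finding (DC / TMD". Methods of data collection describes this examination as including palpation. The number of pressure-pain points is a secondary outcome, so its own model already uses its baseline value.

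The plan treats jaw dysfunction as relevant. It stratifies by sex because "gender is a strong predictor of sleep disorders and also temporomandibular dysfunctions", and it likens the expected side effects to the symptoms of patients with temporomandibular dysfunction. By pain grade, the exclusion criteria remove only GCPS grades 3 and 4. Temporomandibular dysfunction as such is not excluded.

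**The concern.** Sex enters partly as an indirect marker of jaw dysfunction, while the direct measure of that dysfunction stays out of the primary model. Entry does not require pain, so many baseline scores may be 0. A score of 0 cannot separate a healthy jaw from one that is tender on palpation but not painful at that moment. If tenderness predicts later pain under the device, the variation it explains stays in the residual and some power is given up. The timing also matters: a covariate added after the data have been seen would look like selective adjustment.

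**Working it through.** **1. The plan's own figure.** Inputs from Sample size estimation: "To determine a mean difference of 1 level (standard deviation of 2"), "Wilcoxon-Mann-Whitney test with a two-sided $\alpha = 0.05$, a power = 0.90", logistic distribution, and "they must each comprise 78 patients".

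- Two-sample comparison of means: 2 × (1.960 + 1.282)² × 2² / 1² = 84.1, so 85 per group.
- Asymptotic relative efficiency of the Wilcoxon test under the logistic distribution: π²/9 = 1.097. Then 85 / 1.097 = 77.5, so 78.
- The noncentral t version with the same efficiency also gives 78, with power 0.902.
- Dropout: 156 / (0.9 × 0.9) = 192.6, so 193, or 194 for equal groups.

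The figure reproduces. It uses no covariates, so it does not depend on which ones are in the model.

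**2. What one more covariate could add.** Let r be the correlation of baseline pain with the outcome. Let p be the partial correlation of jaw status with the outcome, given the covariates already in the model. The documents give neither, so both are assumptions. The residual variance is multiplied by (1 − r²)(1 − p²), and the standardised effect becomes 0.5 / √[(1 − r²)(1 − p²)]. Example with r = 0.3 and p = 0.3: 0.91 × 0.91 = 0.828, and 0.5 / √0.828 = 0.549. Power at 78 per group:

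| p | r = 0 | r = 0.3 | r = 0.5 |
|---|---|---|---|
| 0 (no jaw term, or no added value) | 0.902 | 0.926 | 0.964 |
| 0.1 | 0.905 | 0.929 | 0.965 |
| 0.2 | 0.913 | 0.936 | 0.969 |
| 0.3 | 0.926 | 0.947 | 0.976 |
| 0.4 | 0.944 | 0.961 | 0.984 |

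The largest gains, at p = 0.4, are 4.2, 3.5 and 2.0 points. On the linear scale the standard error falls by 1 − √(1 − p²): 0.5% at p = 0.1, 2% at 0.2, 4.6% at 0.3 and 8.3% at 0.4. In an ordinal model a prognostic covariate moves the conditional odds ratio away from 1 rather than simply shrinking its standard error, so power is the better measure.

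**3. Check in a proportional-odds model** with 156 patients, r = 0.3 and 600 runs per setting. Power without and with jaw status was 0.920 and 0.917 (p = 0.1), 0.918 and 0.933 (p = 0.2), 0.930 and 0.947 (p = 0.3), and 0.890 and 0.945 (p = 0.4). The simulation error of each figure is about 0.01. The last gap, 5.5 points, exceeds the formula's 3.5, mainly because the figure without jaw status came out below the formula's 0.926. I put no weight on that excess.

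**4. Check with the full model** at the plan's effect of 0.5 SD, with 1,200 paired runs. There are 14 coefficients: device 1, baseline 1, sex 1, age 2, centre 6 (seven clinics), education 3. The three for education are an assumption, because the plan gives no levels. A latent jaw-pain trait is assumed to correlate with pain and with tender-point count at 0.3/0.3, 0.5/0.4, 0.6/0.5, 0.7/0.6 and 0.8/0.7. Gains in power, in points:

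- Pain with mean 4 and SD 2: 0.1, 0.6, 2.2, 1.4, 1.3 (paired standard error about 0.5).
- 70% of pain scores at 0, tender points without a floor: 0.3 to 4.0.
- 70% zeros in both pain and tender points: −0.7, 0.0, 0.3, 1.1, 1.8 (standard error 0.4 to 0.7).

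A separate simulation at the same effect gave about 1 to 2 points under the plan's distribution and about 0 to 4 with 70% zero pain scores.

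**The case against.** The strongest reply is that the plan contains no error here. It prespecifies the stratification factor, centre, age and the baseline value of the outcome, and baseline pain is the covariate tied most directly to later pain. The documents give no evidence that tender points predict pain beyond it. The argument from zero scores also cuts both ways: if most patients start without pain, most may start without tender points, and the gain is then hard to tell from zero except at the strongest correlations. All of this stands, and it limits the point to an optional improvement.

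A reader might infer more, and the documents do not support it:

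- **Bias, or imbalance left uncorrected.** Allocation is randomised, the confidence interval allows for chance imbalance, and baseline pain corrects part of it.
- **A sample size at risk.** The 78 per group rests on an unadjusted test.
- **A gain of about 6 points.** In a simulation with a log odds ratio of 0.75, 70% zeros and the strongest correlations, power rose from 0.760 to 0.818. But a difference of 1 with SD 2 on the logistic scale implies 0.5 × π/√3 = 0.907, so 0.75 is a smaller effect than the plan's and leaves more room for power to rise.
- **School education should go.** It is not named among the baseline data and no reason is given for it. However, the plan lists only the main contents of the study file, and the case report form is not shown.
- **Maximum protrusion should be added.** The inclusion criterion gives only a threshold, "Mandible protrusion of min. 5 mm possible (titration starts at 5 mm"). No section says that the maximum is recorded in millimetres, and advancement is titrated after the start.

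**Conclusion.** The point holds as a small, optional gain in efficiency. The primary model omits baseline jaw status although a standardised examination supplies it before randomisation. At the plan's effect and 156 evaluable patients, one added term is worth about 0 to 4 points of power. The upper end needs a partial correlation near 0.4, or many zero pain scores together with a tender-point count that still varies. If tender points add nothing beyond baseline pain, there is no gain. Every figure above zero rests on assumed correlations, so the documents do not show that precision is actually lost. The validity of the primary analysis and the stated 90% power are unaffected.

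**What to change.** In Statistical evaluation, add the baseline number of pressure-pain points as one further covariate for the primary outcome, and state how it enters (for example, as a single linear term). Do this before the database is opened. The secondary model for pressure-pain points already contains this baseline value and needs no change.

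The cost is one line of text and one coefficient. On the count above, the model goes from 14 to 15 coefficients, or from 156/14 = 11.1 to 156/15 = 10.4 evaluable patients per coefficient. No new examination or visit is needed. The reported odds ratio will then also be conditional on baseline tenderness, which the text should say.

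Separately, the sponsor should confirm where school education is recorded. Removing it, or adding maximum protrusion, is not part of this change.

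### The set called intention-to-treat appears to require a fitted splint as well as assignment, so randomised patients can leave it after their allocation is known

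*Combined protocol and SAP*

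**What the plan says.** Statistical evaluation defines two analysis sets.

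- Intention-to-treat: "The intention-to-treat analysis set includes all patients assigned to one of the two groMAD and the built-up track".
- Per-protocol: this "set includes all patients with supported splints, primary target size data at 24 months and no relevant deviations from the study protocol".

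On missing data the same section says: "Sensitivity analyzes are performed with replacement of missing values via multiple imputation". It does not say which set carries the primary analysis.

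The order of events is set out in three earlier sections.

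- Randomization: "The randomized grouping into blocks at a ratio of 1: 1 takes place over sealed envelopes containing the allocation key for the respective MAD".
- Impression taking: "Subsequently, the upper and lower jaws are molded to make the respective therapeutic splints and the protrusion registrations are taken".
- Integration of the MAD, headed as the start of treatment: the laboratory-made device "is integrated (with a mandibular protrusion of 5 mm) and checked for a comfortable fit".

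Study design leaves the examiner unblinded and blinds the patient and the statisticians. The primary outcome is the change in orofacial pain on the 0-10 NRS once the device has been applied.

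**The concern.** An intention-to-treat set keeps every randomised patient in the arm assigned, because only that full set has the balance that randomisation provides. Here a second condition seems to be added that can be met only some time after the envelope is opened. Between envelope and fitting a patient may withdraw, refuse the device at the fitting visit, or for another reason never receive it. Such a patient is then outside both defined sets.

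The dentist knows the device throughout this interval. The bite preparation also differs by arm: a 5 mm incisor distance for the F-MAD, and the lowest possible incisor distance for the H-MAD (Treatment groups 1 and 2). Non-fitting therefore need not be equally frequent, or have the same causes, in the two arms. What is at stake is whether the comparison of pain between devices remains a comparison of randomised groups.

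**Working it through.** **1. The wording.** 'groMAD' looks like 'groups' after a search-and-replace of UPS by MAD; an unreplaced F-UPS survives at the end of the Abstract. The Abstract also renders the Herbst hinge as an autumn hinge, which shows a literal translation from German. The German word for splint also means track, so 'built-up track' most plausibly means an inserted splint. The per-protocol set has its own splint condition plus 24-month data and adherence to the protocol. On this reading the plan contrasts a fitted set with a worn-and-complete set, and neither contains all randomised patients.

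**2. The gap.** The sequence is envelope, impressions and registrations, manufacture, fitting. Control appointments are timed from incorporation or from the start of therapy, so a never-fitted patient has no scheduled NRS rating. No section says how such patients are followed, reported or analysed. Multiple imputation is planned as a sensitivity analysis, and nothing says that it extends to patients outside the set.

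**3. The plan's own figures reproduce.** Inputs from Sample size estimation: difference 1, SD 2 (d = 0.5), two-sided alpha 0.05, power 0.90, Wilcoxon-Mann-Whitney test with logistic parent.

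- The asymptotic relative efficiency is pi²/9 = 1.0966. A noncentral t calculation with n × 1.0966 gives power 0.898 at 77 and 0.902 at 78 per group, so 78.
- Dropout: 156/(0.9 × 0.9) = 192.6, so 193. The plan's chain 194 − 20 − 18 = 156 also closes.

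**4. Loss of numbers.** The unfitted share f is an assumption and comes on top of the planned dropout. Set size = 194 × (1 − f); at 24 months, multiply by 0.81.

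| f | set size | at 24 months | power |
|---|---|---|---|
| 2% | 190 | 154 | 0.90 |
| 5% | 184 | 149 | 0.89 |
| 10% | 175 | 141 | 0.87 |

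The loss of power from smaller numbers is minor.

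**5. Selection.** Suppose a share q of one arm is never fitted and those patients would have a mean pain change h points from their arm's mean. The mean of those who remain shifts by q × h/(1 − q). For example, 0.05 × 2/0.95 = 0.105. Power is at 78 per group if the shift reduces the planned difference, with d = (1 − shift)/2. Both q and h are assumptions.

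| q | h | shift (NRS points) | power |
|---|---|---|---|
| 2% | 1 | 0.02 | 0.89 |
| 2% | 2 | 0.04 | 0.88 |
| 5% | 1 | 0.05 | 0.87 |
| 5% | 2 | 0.11 | 0.83 |
| 10% | 1 | 0.11 | 0.82 |
| 10% | 2 | 0.22 | 0.72 |

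If both arms lose the same share with the same h, the two shifts cancel. If h has the opposite sign, the shift enlarges the difference instead of reducing it.

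**The case against.** Four objections carry weight.

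- **The reading is inferred from corrupt English.** This stands. It is the likeliest reading, but the sponsor should confirm it. If something else was meant, the sentence still cannot be applied as printed.
- **The outcome is pain once the device is applied, which has no direct meaning for someone never fitted.** This stands as a defence of a fitted set, provided that set is named as modified intention-to-treat. It does not justify the name now used.
- **The route to device-dependent loss is narrow.** Patients are blinded and cannot feel the device before fitting. Starting protrusion is 5 mm in both arms, and eligibility is checked at baseline. Anyone who stops tolerating the device after fitting stays in the set. What remains is refusal at the fitting visit or a decision by an unblinded dentist. Such loss is possible but not shown.
- **Multiple imputation is already planned.** It does not close the gap. A standard missing-at-random model built on fitted patients gives unfitted ones values like those of similar fitted patients in their arm, so it would barely move the estimate.

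A reader might go further and infer that the exclusion biases the result towards no difference, because the least tolerant patients would be lost from the bulkier F-MAD. The documents do not show this. It also depends on which pain is meant. Pain had the device been worn might be high, but the actual pain of someone who never wore it need not be, and including such patients could then shrink the difference. A reader might also infer that dentists can use the rule to escape an allocation, but no section gives them a route to withhold the allotted device.

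**Conclusion.** The concern holds in a limited form. As most plausibly read, the set labelled intention-to-treat is a modified one. Randomised patients who are never fitted leave it after the examiner knows the allocation, and nothing elsewhere in the plan brings them back. This opens the comparison to selection, in a direction the documents do not fix.

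Under the assumed 2% to 10% unfitted in one arm and a 1 to 2 point difference, the shift is about 0.02 to 0.22 NRS points, from negligible to roughly a fifth of the planned difference. No unfitted rate is given, so this is an illustration and not an estimate. A larger figure can be produced: 8 of 97 patients lost, each 4 points above the rest, gives 8/97 × 4 = 0.33. That requires a gap of two of the plan's own SDs and loss counted in one arm only, and the documents support neither.

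That this set carries the primary analysis is itself an inference from its name, its place before the per-protocol set and the label 'sensitivity' on imputation. A reader might take it as stated, but it is not. The sample size of 194 is not affected.

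**What to change.** 1. Confirm the definition against the original-language text.
2. Define intention-to-treat as all randomised patients in the arm assigned, whether or not a splint was fitted, and state that this set carries the primary analysis.
3. Ask never-fitted patients who still consent for the single NRS rating at the planned visit times, counted from randomisation or from the planned fitting date.
4. Impute only what is still missing, and add a sensitivity analysis under a less favourable assumption that is not missing-at-random.
5. Report the number of unfitted patients and the reasons, by arm.
6. Rename the present set 'fitted (modified ITT)' and keep it as supportive, since it matches an outcome defined after the device is applied.

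The cost is a few sentences in the plan, a few extra NRS contacts, some imputed values and slight dilution of the effect.
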